#### 6.6 Locations/Facilities

All work and data storage occurs on the online venues mentioned: OneDrive, REDCap, Actigraph Actilife software, web application programming interface (API) platforms (Dexcom, Fitbit, GlucoseZone), researcher dashboard (Keto-Mojo, Ilumivu, Qualtrics), or user dashboard (InPen) in accord with Yale Information Technology Services protocols (Table A1).

The PI has office space at [name].

August 13, 2024 Version #7

# 7 Statistical Design

#### 7.1 Sample Size Considerations

This is a pilot study with primary objectives to test feasibility and acceptability, for which a typical sample size is 10-40 participants¹. Within this range we chose 24 participants to first ensure thematic saturation of interviews (aims 1-2, 2-3), and second achieve adequate power for one of the secondary objectives, specifically hypothesis 2-1-1. Based on my past retention and adherence among sedentary adults with and without T1D (88% participants completed, they provided 83% of ecological momentary assessments on longer surveys than the present study, 90% continuous glucose monitor wear, and 95% accelerometer wear) I expect 21 completers with an average of 50 complete observations each over T1-T2. Thus, using previous psychometrics of the CRAVE wants and aversions (.28/.39 ICC, 9.9/12.3 total variances) I expect design effects of 14.21/20.11 and standard errors of 0.37/0.48, yielding 91%/81% power to detect predictors having ≥ .34 correlation (e.g., pleasure, fear of hypoglycemia). For other secondary objective hypotheses (2-1-2, 2-2-1, 2-2-2) the study is not designed to detect statistical significance but calculate effect sizes (Cohen's f²) for purposes of determining whether the WANT, SCT model, or both generate a signal for prediction of physical activity behavior.

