# Rationale for determining real-time mechanisms underlying physical activity behavior and T1D-related barriers.

Fear of hypoglycemia has been measured as a "trait" (i.e., personality-specific) but in just one study as a "state" (i.e., situation-specific). Participants reported their state fear of having hypoglycemia over the next 12hr. Responses had significant intraindividual variation and correlation with the related construct of blood glucose variability, indicating the need to further study fear of hypoglycemia as a state variable. Glycemic destabilization meanwhile is recognized to cause intense symptoms that acutely preclude physical activity, but no study has addressed the possible impact of more nuanced changes. E.g., downward-trending glucose could affect motivation to be active even if not projecting an excursion outside the clinically safe range.

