### **SECONDARY**

Hypothesis 2-1-1: Fear of hypoglycemia and blood glucose trends over the past 3 hours will predict momentary motivation states for physical activity (timepoints T1-T2).

Hypothesis 2-1-2: Fear of hypoglycemia and glycemic metrics over the past week will predict motivation states for physical activity over the past week (timepoints T0-T2).

Hypothesis 2-2-1: Motivation states for physical activity over the past week will predict physical activity behavior change and adherence over the 4-week intervention period (T0-T1).

Hypothesis 2-2-2: Motivation states for physical activity over the past 3 hours will predict physical activity maintenance, over the 2 weeks following the intervention (T1-T2).

Protocol Number 2000035846

August 13, 2024 Version #7

Hypothesis 2-3: We expect interview themes among the proposed T1D population will include perception of connection among glycemic variation, fear of hypoglycemia, motivation states for physical activity, and performance of physical activity.

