# STUDY PROTOCOL Social Behavioral Template

# **6 Study Methods/Procedures**

6.1 Study Procedures

Table 1. Visit Schedule

	Pre-screening (Pre-consent)	Visit 1 Day 1	Visit 2 Day 8 ±7	Visit 3 Day 15 ±7	Visit 4 Day 22 ±7	Visits 5 Day 29 ±7	Visit 6 Day 36 ±7	Visit 7 Day 43 ±7	Visit 8 Day 50 ±7	Visit 9 Day 57 ±7	Visit 10 Day 64 ±7	Unscheduled Visit
Screening Phone Call	X											
Contact primary care provider for confirmation	X											
Informed Consent		X										
Demographics		X										
Clinical history		Χ										
Blood pressure			X	X	X	X	X	X	X	X	X	
Monitor symptoms		X	X	X	X	X	Х	X	X	X	X	
Devices			•				'				-	
InPen (if multiple daily injection user)			Continuou	ıs							>	
CGM			Continuo	ıs							>	
Fitbit			Continuo	ıs							>	
Morning survey monitoring daily living (Appendix 8a)			Continuou	ıs							>	
Actigraph GT9X (hip during day, wrist during night)			Continuou	IS	>				Continuous		>	
Intervention												
Mobile App					Continuou	s			>			
Outcome Evaluation											·	
Interview on App Features						X	X	X	X			
Exit Survey on App Features									X			

August 13, 2024 Version #7

Momentary Surveys on Motivation States									5x/day		>	
Weekly Survey on Motivation States			X	X	X	X	X	X	X	X	X	
Interview on Motivation States											X	
Adverse Events Reporting							-					
Adverse Events Reporting			X	X	X	X	X	X	X	X	X	X
Total Time (minutes)	15	30	45	35	65	65	65	65	85	35	80	15

\*The total time commitment for the study is the sum of these visits (575min) + mobile surveys (2min/survey \* 5 surveys/day \* 14 days = 140min) = 715 min, along with the target 150 minutes of exercise per week during the intervention and follow-up (150 min/week \* 6 weeks = 900min), for a total of 1625min or 27 hours.

[figure not shown]

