#### 7.2.1 Secondary Objective Analyses (if applicable)

All statistical models for secondary objectives 1 and 2 will estimate intraclass correlation coefficient (ICC) to assess the proportion of variance explained by participant ID.

Secondary Objective 1 (STATISTICAL, MULTILEVEL MODELING). Examine whether recognized T1D-related physical activity barriers (fear of hypoglycemia, glycemic variation) predict momentary and long-term variation in motivation states for physical activity

**Hypothesis 2-1-1. Momentary predictors of motivation states.** We will develop two multilevel models for the dependent variables of want and aversion for physical activity (CRAVE 2-item "right now") respectively. The independent variables and covariates (Table 2) will be separated into momentary states for level 1, daily states for level 2, and demographics for level 3.

Hypothesis 2-1-2. Week-to-week changes in motivation states. We will develop two generalized linear mixed models for the dependent variables of want and aversion for physical activity (CRAVE 10-item "right now") respectively. A random intercept will incorporate correlations within-subject. We will include long-term assessed independent variables and covariates (Table 2, last column) along with a time categorical variable to estimate the contribution of changes coinciding with intervention (T0 to T1) and maintenance follow-up (T1 to T2).

Secondary Objective 2 (STATISTICAL, MULTILEVEL MODELING). Examine whether motivation states for physical activity predict momentary and long-term variation in physical activity behavior change, adherence, and maintenance resulting from a T1D motivational physical activity intervention.

August 13, 2024

Version #7

Hypothesis 2-2-1 – Predictors of physical activity behavior change and adherence over the intervention. We will develop a generalized linear mixed model for physical activity behavior testing WANT and SCT constructs as independent variables. A random intercept will incorporate correlation within-subject. We will include long-term assessed independent variables and covariates (Table 2, last column) along with a time categorical variable to estimate the contribution of changes from intervention (T0-T1) and maintenance follow-up (T1-T2).

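### Section 7.1: the want design effect of 14.21 does not follow from an ICC of .28 and 50 observations (14.72 does), and the 91%/81% power is printed without alpha, sidedness or test

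*Combined protocol and SAP*

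**What the plan says.** Section 7.1 gives two reasons for enrolling 24 participants: first, thematic saturation of the interviews, and second, adequate power for one secondary hypothesis, 2-1-1. The inputs are past retention ("88% participants completed") and past adherence of 83% for momentary surveys, 90% for glucose-monitor wear and 95% for accelerometer wear. From these the section concludes: "I expect 21 completers with an average of 50 complete observations each over T1-T2". It takes ICCs of .28 (want) and .39 (aversion) and total variances of 9.9 and 12.3 from a cited source, and then states: "I expect design effects of 14.21/20.11 and standard errors of 0.37/0.48, yielding 91%/81% power to detect predictors having ≥ .34 correlation". The Data and Safety Monitoring Plan repeats this in section 8.7 III-A.

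Section 3.2 words the hypothesis without a direction: "Fear of hypoglycemia and blood glucose trends over the past 3 hours will predict momentary motivation states for physical activity". Section 7.2.1 plans two multilevel models, one for want and one for aversion, in which the predictors and covariates "will be separated into momentary states for level 1", with daily states at level 2 and demographics at level 3. None of these sections gives an alpha, a sidedness or a named test for 2-1-1. An alpha of .05 appears only for Hypothesis 1-3-3.

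**The concern.** Two printed inputs and one printed output disagree. The aversion design effect shows which formula and which number of observations were used, and the same calculation does not give the want figure.

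The power pair also cannot be tied to a test from the text alone. This matters because the answer depends on the choice: with these inputs, a conventional two-sided correlation test gives a clearly lower figure for aversion than the printed 81%. Section 7.1 says that the other quantitative secondary hypotheses are not designed for statistical significance, so this is the only secondary hypothesis with a power claim. A null result for want or aversion would be read against that claim.

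**Working it through.** **Inputs (section 7.1 unless noted).** Completers: 24 × .88 = 21.12, stated as 21. Prompts per person: the Table 1 footnote in section 6.1 ("5 surveys/day \* 14 days = 140min") implies 5 × 14 = 70. Complete observations: 70 × .83 × .90 × .95 = 49.7, stated as 50. Total observations: 21 × 50 = 1,050. ICC .28/.39, total variance 9.9/12.3, r = .34.

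**Design effect, 1 + (m − 1) × ICC with m = 50.**
- Aversion: 1 + 49 × .39 = 20.11. This matches the printed figure exactly and so identifies the formula and m.
- Want: 1 + 49 × .28 = 14.72. The printed figure is 14.21.

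**Can rounding explain it?** An ICC between .275 and .285 gives 14.48 to 14.97. Letting m fall to 49.5 as well gives 1 + 48.5 × .275 = 14.34 at the lowest. To reach 14.21 requires ICC = 13.21/49 = .2696, which would print as .27, or m = 1 + 13.21/.28 = 48.18. The second option fails because aversion would then be 1 + 47.18 × .39 = 19.40, not 20.11.

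**Effect of the slip.**
- Want effective n: 1,050/14.21 = 73.9, against 1,050/14.72 = 71.3.
- Want standard error: √(9.9 × 14.21/1,050) = .366, against √(9.9 × 14.72/1,050) = .373. Both print as 0.37.
- Aversion effective n: 1,050/20.11 = 52.2. Its standard error is √(12.3 × 20.11/1,050) = .485, against a printed 0.48, which is a rounding-level difference.

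**Power at r = .34 and alpha .05, from these effective sample sizes.** Fisher z power is Φ(atanh(r) × √(n − 3) − z). Wald power is Φ(r√n/(1 − r²) − z), that is, with SE = (1 − r²)/√n.

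| Test | Want, 14.21 | Want, 14.72 | Aversion, 20.11 |
|---|---|---|---|
| Exact correlation, one-sided | 91.3% | 90.4% | 80.7% |
| Fisher z, one-sided | 90.9% | 90.0% | 79.9% |
| Wald, two-sided | 91.1% | 90.1% | 79.3% |
| Exact correlation, two-sided | 85.1% | 83.9% | 70.8% |
| Fisher z, two-sided | 84.7% | 83.3% | 70.0% |

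The first row, with the printed design effects, rounds to 91%/81%. The two-sided Wald row comes close. If n is instead backed out of the printed standard errors (9.9/.37² = 72.3 and 12.3/.48² = 53.4), two-sided Wald gives 90.5%/80.2% at r = .34. At r = .342, which also prints as .34, it gives 90.9%/80.8%.

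**How far the two-sided correlation figures apply.** The factor 1 + (m − 1) × ICC treats the predictor as constant within a person. If the predictor has its own ICC, and the design effect is taken as 1 + 49 × ICC(outcome) × ICC(predictor), two-sided .05 exact power for want/aversion is as follows. The predictor ICC is not in the documents, so these values are assumptions.
- Predictor ICC 1.0: 84%/71%
- Predictor ICC .8: 91%/80%
- Predictor ICC .5: 98%/94%
- Predictor ICC .3: 99.9%/99%

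**The case against.** In the plan's favour, the printed power can be reconstructed, the one proven error moves want by about a point and aversion not at all, and N = 24 rests first on interview saturation. All of that stands, and it keeps the point minor.

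Two stronger readings are tempting, and the documents support neither.

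The first is that the plan relies on an undisclosed one-sided test. The one-sided exact test does match both figures, but a two-sided Wald calculation from the printed standard errors also prints 91%/81% once the rounding of r is allowed for. The text does not say which was used, so one-sidedness remains an inference.

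The second is that aversion is really powered at only 71%. That figure belongs to a predictor that never varies within a person, whereas 2-1-1 tests momentary predictors at level 1. Section 1.1 reports of state fear of hypoglycemia in earlier work: "Responses had significant intraindividual variation and correlation with the related construct of blood glucose variability". If the predictor varies within person, the same two-sided test gives more power, possibly above the printed values.

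These arguments do not remove the conflict between 14.21 and .28, or the need to name the test before a corrected power can be printed.

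**Conclusion.** The want design effect is inconsistent with its own inputs in sections 7.1 and 8.7 III-A: 14.72 follows from the printed ICC and m, and 14.21 does not. The documents cannot show whether .28 or 14.21 is the slip. If .28 is right, want power falls from 91% to about 90% on the tests that come close to the printed figures. This part is certain, because the exact match for aversion fixes the formula and m.

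The missing alpha, sidedness and test are a gap in specification. They matter because the choice moves the two figures from about 90%/81% to about 84%/71%. The lower pair assumes a two-sided .05 correlation test and a predictor constant within person, so it is a conservative bound and not an estimate of the planned models' power.

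Severity is minor. The point concerns one secondary power statement, with no effect on N or on any primary objective.

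**What to change.** Edit the power sentence in section 7.1 and its copy in section 8.7 III-A, leaving N unchanged:

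1. Check the want ICC against the cited source. If .28 is right, print 14.72. If 14.21 is right, print an ICC of about .27.
2. State the test, alpha and sidedness actually used. If the test was one-sided, declare that and justify the direction.
3. Reprint the power that follows from the corrected inputs. If it comes from a two-sided correlation test with this design effect, label it a conservative bound for a predictor constant within person. If a predictor ICC is assumed instead, state it and give its source.

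The cost is a sentence or two in two places, with no change to design or conduct. The drawback is that a two-sided correlation figure would look less favourable and is probably pessimistic for momentary predictors, while the predictor-ICC route adds an assumption that has to be supported.

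### The 91%/81% power for Hypothesis 2-1-1 uses the variance inflation for a mean or an unchanging person-level predictor, so it is not the power of the planned test of momentary predictors

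*Combined protocol and SAP*

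**What the plan says.** Section 7.1 gives thematic saturation of the interviews as the first reason for 24 participants and adequate power for Hypothesis 2-1-1 as the second. It assumes: "I expect 21 completers with an average of 50 complete observations each over T1-T2". From CRAVE outcome ICCs of .28 (want) and .39 (aversion) and total variances of 9.9 and 12.3 it continues: "I expect design effects of 14.21/20.11 and standard errors of 0.37/0.48, yielding 91%/81% power to detect predictors" with a correlation of at least .34, naming pleasure and fear of hypoglycemia as examples. Section 8.7 III-A repeats this text.

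Section 3.2 states Hypothesis 2-1-1 in terms of fear of hypoglycemia and glucose trends over the preceding 3 hours. Table 2 in 6.1.1 has both assessed at each of five daily prompts. Section 7.2.1 says that the independent variables and covariates "will be separated into momentary states for level 1, daily states for level 2, and demographics for level 3".

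The source cited for the fear correlation is described in 1.1, and again in 2.1, as finding within-person variation in state fear and "correlation with the related construct of blood glucose variability". Neither section mentions CRAVE in connection with that study.

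**The concern.** A design effect of 1+(m−1)ICC, using the outcome ICC alone, is right for the mean of clustered data or for the slope of a predictor that is constant within each person. For a predictor that moves from prompt to prompt, the person intercept absorbs the between-person variance. The precision of the slope then depends on the within-person residual variance, on how much of the predictor's variance lies between people (its ICC), and on how much the slope differs from person to person. Section 7.1 gives neither the predictor ICC nor the slope variance, and does not say whether .34 is a within-person or a total-scale correlation.

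This is the only secondary hypothesis with a stated power. A reader who takes 91%/81% as the power of the planned test will misjudge what a null result means: too leniently if slopes are common, too severely if slopes vary strongly.

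**Working it through.** **Inputs (7.1 unless noted).** 24 x .88 = 21.1, so k = 21 completers. Five prompts on 14 days (Table 1 footnote) give 70; 70 x .83 x .90 x .95 = 49.7, so m = 50 and there are 1,050 observations. Outcome ICC .28/.39, variance 9.9/12.3, r = .34. Alpha and sidedness are not stated for this calculation. Pairs below are want/aversion.

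**Reproducing the plan's figure.**
- Design effect 1+49 x .39 = 20.11, as stated. For want, 1+49 x .28 = 14.72, against the stated 14.21 (a separate, minor matter).
- Standard errors: √(9.9 x 14.21/1050) = .366 and √(12.3 x 20.11/1050) = .485. These match .37/.48 (the second truncated) and are standard errors of a mean score.
- Effective N: 1050/14.21 = 73.9 and 1050/20.11 = 52.2.
- Power at r = .34 by Fisher z, atanh(.34) x √(N−3) − z: one-sided .05 gives 90.9%/79.9% (91.5%/80.9% by simulating the exact test). Two-sided .05 gives 84.7%/70.0%.

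So 91%/81% is a one-sided test of r = .34 at the effective N for an unchanging predictor.

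**Predictor that changes within person, common slope, two-sided .05.** The predictor ICC is not in the documents and is shown as a range. Two approximations were used.

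(a) Pooled slope, design effect 1+49 x ICCx x ICCy, Fisher z:

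| Predictor ICC | Power, want/aversion |
|---|---|
| 0 to .2 | >99.9% / 99.9% or more |
| .5 | 98.2% / 93.6% |
| .7 | 93.4% / 84.2% |
| .9 | 86.9% / 74.5% |
| 1 | 83.3% / 70.0% |

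(b) Random-intercept model with equal within- and between-person slopes and r = .34 on the total scale. Slope information = k(m−1)(1−ICCx)/(1−ICCy) + (k−1)(ICCx+(1−ICCx)/m)/(ICCy+(1−ICCy)/m). Power exceeds 99.9% for predictor ICC 0 to .8 and is 80%/67% at predictor ICC 1.

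**Smallest detectable effect, purely within-person predictor, common slope, 80% power.** Within-person r = 2.80/√(21 x 49) = 2.80/√1029 = .087. On the total scale this is .087 x √.72 = .074 and .087 x √.61 = .068.

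**Slopes that vary between people.** With slope SD τ in outcome-SD units (assumed), SE² = τ²/21 + (1−ICCy)/1029.
- τ = .3: SE .0706/.0698. Detectable slope 2.80 x SE = .198/.196; dividing by √.72 and √.61 gives within-person r of .23/.25 (normal quantiles).
- Within-person r = .34 means an average slope of .34 x √.72 = .288 or .34 x √.61 = .266. At τ = .4, SE .0912/.0906 gives power 85%/80%; at τ = .5, SE .1123/.1118 gives 69%/62% (two-sided t, 20 df).

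**Person-level predictors.** If .34 is the correlation with the 21 person means, Fisher z gives atanh(.34) x √18 − 1.96 = −.46, or 32% power. If .34 is on the total scale, it implies a person-mean correlation of .34/√(.28+.72/50) = .63 or .34/√(.39+.61/50) = .54, and power 88%/72%. The same printed .34 therefore means very different things on the two scales.

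**The case against.** The strongest defence is that the shortcut errs on the safe side. Treating the predictor as constant within person is the worst case in a random-intercept model, so the claim of adequate power survives under a common slope. The hypothesis is secondary in a pilot, and interview saturation is the first reason given for 24. All of that stands.

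A reader might infer that 24 is too few, or that power should be dropped as a reason for 24. The documents support neither: with a common slope the corrected power is higher than stated, which strengthens that reason. A reader might also seize on 32% as the true power. That figure applies only if .34 is a correlation with person means, a smaller effect than .34 on the total scale, and the predictors named in 2-1-1 are momentary.

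It is also fair to say that the corrected figures are simplified. They omit the day level in 7.2.1, serial correlation between prompts and overlap with the many Table 2 covariates, all of which could reduce precision. The .09 is therefore a best case, and 91%/81% is not far from what moderate-to-strong slope variation gives. But agreement at one assumed slope SD does not make the formula right, and the plan declares no such assumption.

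On the .34 for fear, the cited study may report more than the protocol describes, and that cannot be checked here. The pleasure example is cited to the same source as the CRAVE psychometrics and is not challenged.

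**Conclusion.** The point holds: the stated 91%/81% is not the power of the level-1 test planned for Hypothesis 2-1-1. It describes an unchanging predictor, tested one-sided at .05.

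The direction matters. With a common slope the statement is conservative. Power falls materially below it only if slopes vary strongly (SD about .4 or more, larger than the average slope of .27 to .29 that within-person r = .34 implies) or if the predictor is nearly trait-like and tested two-sided. The error gives no ground for changing the sample size.

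These conclusions rest on 21 x 50 observations, the outcome ICCs in 7.1, two-sided .05, and assumed ranges for predictor ICC and slope SD, neither of which the documents give. The .34 for fear of hypoglycemia is, as far as the protocol shows, an assumption: its source is described only as relating fear to glucose variability.

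**What to change.** In 7.1 and 8.7 III-A, replace the power sentence with power for the level-1 slope. State alpha and sidedness, whether r is within-person or total-scale, the centering, and assumed ranges for predictor ICC and slope SD.

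For 21 x 50 and two-sided .05, the text could report a smallest within-person r at 80% power of about .09 with a common slope and about .23 to .25 at slope SD .3. It could add power at within-person r = .34 of about 85%/80% at slope SD .4 and 69%/62% at .5. A short simulation of the three-level model would be better still.

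If person-level predictors are mentioned, report them separately with the scale named (about 32% if .34 is with the 21 person means). Label .34 for fear of hypoglycemia as an assumption and give a range. Keep the rationale for 24, restated with the corrected level-1 power.

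The cost is wording in two places and, optionally, a simulation. Sample size and conduct do not change.
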